In addition to the specific gene expression assays for neurosteroidogenic enzymes performed by [name], We will also perform “whole transcriptome shotgun sequencing” in each sample collected across both conditions, which measures the presence and quantity of RNA (related to the entire genome) in a given sample at a given moment. This will be used to test hypotheses regarding the effects of the manipulation on expression of genes coding for all neurosteroidogenic enzymes (not just those measured by [name] using qPCR), GABA-A receptor subunits, and inflammatory cytokines. These analyses will also be performed in-house at the University of Illinois.

Neuroactive steroids for HC participants (Aim 3 substudy).

Neuroactive steroids, mRNA, and genome sequence collection will be identical in the substudy as described above.

Smartphone-Based Assessments

Daily Symptoms Survey (3 minutes each evening throughout the 4-month Study). Each evening throughout the four months of the study, participants will complete the following self-report scales. First, the Daily Rating Form (DRF)⁵⁵, capturing hormone-related symptoms listed in the DSM-5^{118(p5)} (depression, hopelessness, worthlessness, anxiety, mood swings, rejection sensitivity, anger/irritability, interpersonal conflict, difficulty concentrating, lack of interest, insomnia, hypersomnia, overeating, lack of appetite, emotional overwhelm (hyperarousal), feeling out of control, fatigue, and physical discomfort). In addition to the DRF, participants will complete the Brief Agitation Measure (BAM)⁵⁴, a 3-item measure that taps into feelings of agitation (e.g., “I felt so stirred up inside that I wanted to scream”; hyperarousal) as well as dimensional ratings of the three highest-loading items from the Beck Hopelessness Scale¹⁷ (e.g., “The future seems dark to me”). This daily survey will provide an integrated rating of the patient’s symptoms across the entire day, consistent with methods used in seminal experiments of hormones and mood^{30,119,120}. Medication adherence, stressor exposure¹⁹, medication, drug, and alcohol use, sleep, pain, illness, and exercise will be recorded; any additional probing to clarify these online responses will be take place during the following day’s daily safety call.

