history indicative of increased breast cancer risk or thromboembolic disorders; 5) the frequent assessment of side effects at every phone call; 6) provision of a drug information sheet with the instruction to call the study doctors immediately if any of the following symptoms are experienced: abnormal or prolonged vaginal bleeding, severe headaches, changes in vision or speech, dizziness or faintness, pains in calves or chest, or sudden shortness of breath; 7) banking a prescription for a back-up, additional 3 pills with the investigational drug service for each participant in an active condition will prevent participants from missing study medication doses on days they are in the lab should they forget to bring their study medication with them to the lab visit; 8) the development of a safety monitoring plan (see below); and 9) monitoring for adverse events by a Data and Safety Monitoring Committee.

2) Effects of the Ovarian Hormone Stabilization Protocol on Mood and Suicidality (for primary experimental group; N/A for HC group).

The following measures will be taken to mitigate any negative impact of the experiment on mood or suicidality:

Depressive symptoms and suicidality will be monitored during a daily evening telephone call during each condition and will also be measured and monitored via smartphone surveys. These daily calls will be carried out by trained research assistants, and the PI will be on-call during these calls. In the case of **(A) severe mood changes** (defined below) or **(B) imminent risk for suicide attempt (requiring inpatient hospitalization)**, participation will be discontinued and the individual will be referred for an appropriate level of psychiatric care. Protocols for assessing severity of mood symptom changes, evaluating suicide risk, and discontinuation and referral are described below.

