Protocol for Assessing Emergence of Severe Mood Changes. Because they will be recruited for recent suicidality, participants are expected to show elevated baseline levels of mood symptoms. Therefore, the emergence of severe mood symptoms will be defined as three days of daily depression scores (defined as depression, hopelessness, and worthlessness/guilt on the daily symptom record as defined in the research strategy) that are 1) severe or extreme in nature (i.e., above “moderate” on the response scale), 2) at least 50% increased over their self-reported trait levels of depression (as defined by mean scores on these items across the baseline month), 3) maintained for three consecutive days, and 4) a clinical interview must reveal that this worsening of mood is significantly impacting functioning in relationships or ability to engage with work or school. Should such an acute, impairment-related worsening of depression persist for three days, the **Protocol for Discontinuation and Referral** described below will be followed to remove the participant from the study and ensure proper engagement with their mental health provider at the appropriate level of psychiatric care.

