If a participant must be referred for emergency treatment (via emergency services/911 safety check, or walking the patient to the emergency room) at any point in the study, the blind will be broken for the participant and their study participation will be discontinued. If it is revealed that the participant was currently in the placebo condition, they will simply be referred to their mental health provider (or, as necessary, to the emergency department) for treatment. However, if it is revealed that the participant was currently in an active hormone stabilization condition, the supervising physician ([name]) will oversee a gradual tapering of the hormonal intervention and the patient will be referred to their mental health provider (or, as necessary, the emergency department) for treatment.

Protocol for Discontinuation and Referral. The protocol for discontinuation and referral is as follows. First, if the patient needs immediate inpatient evaluation or care, we will follow the protocol outlined in the UWRAP (see Appendix) to facilitate referral to emergency department (either via coordination with the emergency contact, by involving emergency services to perform a safety check at the participant's home, or by recruiting the help of UIC security to escort the patient from the outpatient psychiatry offices to the UIC emergency department. While the patient's immediate need for care is being attended to, the study staff will contact the investigational drug pharmacy and the blind will be broken for the study staff, the PI, and the participant. The participant will be notified that their study participation is discontinued and provided with instructions for either tapering medication (if active medication was being taken) or to follow up as needed with outpatient providers. If it is revealed that the participant was currently in an active hormone stabilization condition, [name] will oversee (or communicate with the participant's physician to recommend) a gradual tapering of the hormonal intervention.

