Paper Document Safety. Paper documents containing PHI include those used to register patients in the UIC vendor system to be paid for their participation, which include SSN, address, and name, as well as the SCID-5, which includes date of birth and other demographic information. These documents will be digitized (see notes regarding digital data protections above) and shredded. Any paper documents that have not yet been digitized (e.g., SCID-5 interviews awaiting data entry) will be stored in a locked file drawer in the PI's locked office until they are digitized (see above). Only the PI and the project manager will have keys to this file drawer. Once digitized, all paper documents (except consent forms) will be immediately shredded per UIC protocol for protected health information. Consent forms will be kept in a locked file drawer in the PI's office as per UIC ethics protocol.

Data Monitoring and Report Generation. Each month, the project manager will generate a report from the database, including information about participant flow, demographics, and data completeness. This report will be sent to the PI and all Co-Is for review. Reports will also include detailed (but deidentified) information about any Adverse Events (AEs) (e.g., suicide risk elevation) and follow-up procedures.

Monitoring and Reporting of Mood Changes, Suicide Risk, and Adverse Events. The PI will supervise the clinical postdoctoral fellow as well as the project manager in monitoring changes in suicidal risk and mood symptoms obtained from laboratory visits, daily online surveys, and daily telephone risk screenings. Research staff will be specifically trained to identify significant changes in mood or suicidality in various assessments (see protocol in Protection of Human Subjects section), which will be reported immediately to the PI and further monitored for the duration and impairment criteria described in the Protection of Human Subjects Section (i.e., symptoms must interfere with either relationships or occupational health, and must remain elevated for three days). As described above, participants who experience significant deterioration in mood or who are judged to be at imminent suicide attempt risk will be discontinued from the

protocol and referred for an appropriate level of psychiatric care.

In addition, specific events to be reported to the data safety and monitoring board (DSMB) will be defined by the DSMB at their first meeting prior to the start of the research.

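### Minor safety point: a required 50% rise over baseline puts the written mood ground for discontinuation out of reach for participants whose baseline is already high on the scale, and no exception is given

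*Protocol*

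**What the plan says.** Protocol 7.0, in its measures to limit harm to mood and suicidality, gives two grounds for stopping: (A) severe mood changes and (B) imminent risk of a suicide attempt. On either, "participation will be discontinued and the individual will be referred for an appropriate level of psychiatric care".

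Ground A is defined in the paragraph Protocol for Assessing Emergence of Severe Mood Changes. It uses three daily items (depression, hopelessness, worthlessness or guilt) and four conditions joined by 'and':

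1. Scores are "severe or extreme in nature", explained as above 'moderate'.
2. Scores are "at least 50% increased over their self-reported trait levels of depression", with trait level "as defined by mean scores on these items across the baseline month".
3. This lasts three days in a row.
4. In addition, "a clinical interview must reveal that this worsening of mood is significantly impacting functioning" in relationships, work or school.

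The paragraph opens by saying that raised baseline mood symptoms are expected in this sample, and gives that as the reason for defining the rule this way. For the items it points to a research strategy that is not among the documents. The Daily Symptoms Survey text in Protocol 6.0 lists the items ("depression, hopelessness, worthlessness, anxiety, mood swings, rejection sensitivity" and so on) without a response range or coding.

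Protocol 9.0 says that significant mood changes are reported to the PI at once and "further monitored for the duration and impairment criteria described in the Protection of Human Subjects Section". The SAP does not deal with the rule.

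**The concern.** Measuring worsening against the participant's own baseline is a sensible choice in a sample recruited for recent suicidal ideation, because an absolute threshold alone would flag people at their usual level. A proportional rise on a bounded scale, however, runs out of room as the starting point goes up. Beyond some baseline the required score lies above the top of the scale. Because the conditions are joined by 'and', nothing found under the other three can make up for that. The rule therefore becomes harder to meet as baseline severity increases, and the eligibility criteria in Protocol 4.1 set no upper limit on depression severity.

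What is at stake is one written ground for mandatory discontinuation and referral. The case that falls through is severe, impairing worsening of depression without imminent suicide risk, since ground B covers only the latter.

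**Working it through.** The plan gives no figure of its own to reproduce. The check is algebra on condition 2, followed by a search for an exception.

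**Inputs.** From Protocol 7.0: a required rise of at least 50%, a reference equal to the participant's baseline-month mean *b*, and a response scale with a top category, maximum *M*. The numerical range, its floor *L*, the coding and the use of a three-item mean are assumptions, because the documents do not give them.

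**Step 1, raw-score reading.** Condition 2 needs a score *s* ≥ 1.5*b*, and *s* cannot exceed *M*. It can be met only if 1.5*b* ≤ *M*, that is *b* ≤ *M*/1.5 = two thirds of *M*.

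**Step 2, rise counted from the scale floor.** The condition becomes *s* − *L* ≥ 1.5(*b* − *L*), so it can be met only if *b* ≤ *L* + (*M* − *L*)/1.5.

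| Assumed range | Cut-off, raw (*M*/1.5) | Cut-off, from floor | Floor cut-off as share of *M* |
|---|---|---|---|
| 0–4 | 2.67 | 2.67 | 67% |
| 1–5 | 3.33 | 3.67 | 73% |
| 1–6 | 4.00 | 4.33 | 72% |
| 1–7 | 4.67 | 5.00 | 71% |

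The reading moves the cut-off, but a ceiling remains under both.

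**Step 3, example (assumed 1–6, raw reading).**
- Baseline 4.0 needs 1.5 × 4.0 = 6.0: attainable only with the top score on all three items, three days running.
- Baseline 4.1 needs 1.5 × 4.1 = 6.15: impossible. Three days at 6 is a rise of 6/4.1 − 1 = 46% and fails.
- Baseline 4.5 needs 6.75: impossible.

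**Step 4, is there an exception?** The texts, taken side by side:
- The severe-mood paragraph in 7.0 lists the four conditions and no alternative to any of them.
- The suicide-risk paragraphs in 7.0 (UWRAP screening, emergency referral, Protocol for Discontinuation and Referral) do not depend on the 50% rise, but they act on suicide risk, not on ground A.
- The hormone side-effect paragraph in 7.0 discontinues participants for clinically significant effects judged due to the hormones. Its examples are physical, and it does not mention condition 2.
- Protocol 9.0 repeats duration and impairment and leaves out the 50% figure, but sends the reader back to the rule in 7.0.

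None of these states that condition 2 is waived at the ceiling.

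**Step 5, a cap on condition 2.** Suppose the required score is the smaller of 1.5*b* and *M*. On the assumed 1–6 scale the rises it would accept above the cut-off are 6/4.1 − 1 = 46%, 6/5.0 − 1 = 20% and 6/5.8 − 1 = 3%. Baseline 4.1 with three days at 5.67 (one item one point short) is a rise of 5.67/4.1 − 1 = 38% and still fails, because 5.67 < 6. At *b* = 4.0 the cap and the present rule require the same score, so there is no jump at the cut-off.

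**The case against.** The strongest reply is that little is lost. Participants still have daily calls with the PI on call, UWRAP screening with its mood-improvement and emergency steps, immediate reporting of mood changes to the PI, required outpatient mental health care, the Welcome Visit safety plan and DSMB review. That stands, and it rules out a stronger reading that a reader might infer: that high-baseline participants are left unprotected or cannot be withdrawn. The documents show only that one written ground is closed to them.

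A second reply is that Protocol 9.0, which names duration and impairment without the 50% figure, lets staff act in practice. It may. But it refers back to the 7.0 rule and is not a clear waiver.

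Third, the scale may be defined in the research strategy. That also stands. The lack of a range in the protocol is not an error in itself, and every raw cut-off above is an assumption. The 7.0 paragraph also leaves open whether the 50% applies to a three-item composite or to each item. Item by item, someone with one high item might still qualify on another.

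It is tempting to say that the gap reaches people with only moderate baselines. If severe and extreme are the two top categories, 'moderate' is *M* − 2 and the raw cut-off lies +0.67 (0–4), +0.33 (1–5), 0.00 (1–6) or −0.33 (1–7) points from it. Only the last assumption puts the cut-off below 'moderate'. The reference is also a mean over a whole baseline cycle, so passing the cut-off means sustained symptoms, not a few bad days. The documents do not support that wider reach.

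Finally, the cap tracks worsening imperfectly: a 3% rise to the maximum passes the numerical test and a 38% rise short of it fails. This is a real limitation, but the interview still has to find impairing worsening before anyone is discontinued.

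**Conclusion.** The point holds as a minor safety improvement. With condition 2 read as 1.5 times the raw composite mean, ground A cannot be met above two thirds of the scale maximum. Counted from the scale floor, the limit is about 71–73% on assumed 1–5 to 1–7 scales. No exception is stated in Protocol 7.0, and 9.0 does not clearly supply one.

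The two-thirds figure depends on the raw composite reading and should not be quoted without it. The number of participants affected cannot be derived, because neither the scale nor a baseline distribution is given, and it may be small. Sample size, power and alpha are not affected.

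**What to change.** Add to condition 2: *or, where a 50% increase would exceed the scale maximum, scores at the scale maximum on all three days*. Leave conditions 1, 3 and 4 as they are, so that the effect is to send such a participant to the interview, which must still show impairing worsening. If the research strategy does not already say so, it would help to note whether the 50% applies to the raw composite.

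The cost is one clause and no new data, since the daily scores and the baseline month are already collected. The downside is that near the ceiling the numerical test becomes weak and the interview carries most of the decision, so a few chronically severe participants could be discontinued near their usual state. For each of them "the blind will be broken for the study staff, the PI, and the participant", hormones would be tapered if active, and a completer would be lost. Recruiting 170 for 90 completers allows 170 − 90 = 80 non-completers. Such cases would come out of that number, which ordinary dropout may also use.

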If a participant must be referred for emergency treatment (via emergency services/911 safety check, or walking the patient to the emergency room) at any point in the study, the blind will be broken for the participant and their study participation will be discontinued. If it is revealed that the participant was currently in the placebo condition, they will simply be referred to their mental health provider (or, as necessary, to the emergency department) for treatment. However, if it is revealed that the participant was currently in an active hormone stabilization condition, the supervising physician ([name]) will oversee a gradual tapering of the hormonal intervention and the patient will be referred to their mental health provider (or, as necessary, the emergency department) for treatment.

Protocol for Discontinuation and Referral. The protocol for discontinuation and referral is as follows. First, if the patient needs immediate inpatient evaluation or care, we will follow the protocol outlined in the UWRAP (see Appendix) to facilitate referral to emergency department (either via coordination with the emergency contact, by involving emergency services to perform a safety check at the participant's home, or by recruiting the help of UIC security to escort the patient from the outpatient psychiatry offices to the UIC emergency department. While the patient's immediate need for care is being attended to, the study staff will contact the investigational drug pharmacy and the blind will be broken for the study staff, the PI, and the participant. The participant will be notified that their study participation is discontinued and provided with instructions for either tapering medication (if active medication was being taken) or to follow up as needed with outpatient providers. If it is revealed that the participant was currently in an active hormone stabilization condition, [name] will oversee (or communicate with the participant's physician to recommend) a gradual tapering of the hormonal intervention.

3) Hormone Side Effects (for primary experimental group; N/A for HC group). As discussed above, we do not expect any adverse side effects associated with the hormonal manipulations outlined in this protocol. However, any patient experiencing clinically significant side effects (e.g., nausea, hypertension, vomiting) deemed by [name] to be due to the hormonal manipulation will be discontinued from the study. The blind will be broken for that participant and their study participation will be discontinued. If it is revealed that the participant was currently completing the placebo condition, they will be informed of this and referred for outpatient medical care. However, if it is revealed that the participant was currently completing the active hormone stabilization condition, [name] will oversee a gradual tapering of the hormonal intervention and the patient will be referred for outpatient medical care.

4) Confidentiality.

For each of the above measurements, participants will be identified by study ID number on all research documents,

electronic data files, and collected specimens. All paper data will be stored in locked cabinets inside locked offices, and electronic data will be stored only on password-protected file servers only accessible from computers in the Psychiatry Department. The file linking the study ID number to identifying information will be kept separate from any study data on a UIC Psychiatry password protected drive. Only study personnel will have access to these data.

Biaffect Data Confidentiality. Sage Bionetworks, the company who stores the behavioral and EMA response data collected by Biaffect and other Apple HealthKit apps, will provide a business associate agreement to ensure continued HIPAA-compliant handling of data. They will not collect information about location or any other identifying information. Nonetheless, to maintain strict confidentiality of the BiAffect Data linked to this study, the research staff will create an anonymous email address for each study participant and create a linked BiAffect account for the study; this email address (which defines the account) will be linked to the participant's study ID for the trial only on a password-protected spreadsheet in the UIC server. Therefore, Sage Bionetworks will process only deidentified data and will not be able to link study data to any individual.

MetricWire Data Confidentiality. Metricwire is the company that will collect the phone sensor data (movement, acceleration) from participant smartphones as an augment to the use of the Biaffect app. A study-generated email address and password will be used to register each participant's phone to the Metricwire App, and collection of IP address will be turned off; these measures eliminate any identifiers from being coded by the Metricwire app. However, Metricwire is HIPAA-compliant and a Business Associate's Agreement is on file with UIC through our laboratory for data collection and storage through this company.

Oura Ring Data Confidentiality. No identifiable data will be collected from the Oura Ring. The serial number of rings given to participants will not be recorded. A premade study email will be used to create an Oura Ring App account. Therefore, no identifiable information will be collected related to the Oura App or Ring.

5) Venipuncture. The use of a trained phlebotomist who is fully trained in safety protocols will minimize any risk associated with venipuncture.

6) Oura Ring. We will exclude participants with epilepsy, pacemakers, and other internal electronic devices to reduce any possible/theoretical risks associated with use of the Oura Ring.

POTENTIAL BENEFITS OF THE PROPOSED RESEARCH TO HUMAN PARTICIPANTS AND OTHERS

This is a mechanistic study to determine the role of ovarian hormone changes in constructs that are relevant to suicidality. There is no direct benefit to the participants other than the benefit of knowing that they are contributing to research on the causes of suicidality.

